4. OBJECTIVES

A. Primary Objectives:

The primary objective of this clinical trial is to evaluate, within the limits of a phase II study, the preliminary efficacy as defined by engraftment, of a regimen consisting of treosulfan and fludarabine followed by allogeneic HCT in patients with nonmalignant inherited disorders.

B. Secondary Objectives:

1. Incidence of non-relapse mortality 200 days and 1 year post-HCT
2. Incidence of grade II-IV acute GVHD
3. Incidence of chronic GVHD – as defined as those patients requiring systemic immunosuppression
4. Donor chimerism on days +28 and +100
5. Assess disease response following HCT
6. Immune reconstitution following HCT
7. Incidence of infections
8. Overall survival

C. Exploratory Objectives:

1. Pharmacokinetic parameters of treosulfan and treosulfan monoepoxide

5. PATIENT SELECTION

5A. Inclusions:

1. Age < 50 years with nonmalignant disease treatable by allogeneic HCT.
2. Patients with a known nonmalignant disease that is not clearly defined will need to be discussed with the protocol PI ([name]) and potentially the Nonmalignant board to determine if they are eligible for HCT on this study.

5B. Exclusions:

1. Patients with Idiopathic Aplastic Anemia and Fanconi Anemia. (Patients with Aplastic Anemia associated with PNH or inherited marrow failure syndromes, except Fanconi Anemia, will be allowed).
2. Patients with the following organ dysfunction:
 - a. With impaired cardiac function as evidenced by ejection fraction < 35% (or, if unable to obtain ejection fraction, shortening fraction of <26%) or cardiac insufficiency requiring treatment or symptomatic coronary artery disease. Patients with a shortening fraction < 26% may be enrolled if approved by a cardiologist.
 - b. With impaired pulmonary function as evidenced by DLCO < 50% of predicted (or, if unable to perform pulmonary function tests, then O₂ saturation < 92% on room air).
 - c. With impaired renal function as evidenced by creatinine-clearance < 50% for age, weight, height or serum creatinine > 2X upper normal limit or dialysis-dependent.
 - d. With evidence of synthetic dysfunction or severe cirrhosis requiring deferral of conditioning as recommended by a gastroenterology specialist.

3. Patients with an active infectious disease requiring deferral of conditioning; as recommended by an Infectious Disease specialist.
4. Patients who are positive for human immunodeficiency virus (HIV).
5. Females who are pregnant or breast-feeding.
6. Patients with a known hypersensitivity to treosulfan and/or fludarabine.
7. Receiving another experimental drug within 4 weeks of initiation of conditioning (day -6) unless approved by the PI.

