Thymoglobulin will be administered intravenously over three consecutive days (days -4, -3, -2) at a dose of 1.0 mg/kg on day -4, and then 2.5 mg/kg on days -3 and -2 for a total dose of 6.0 mg/kg. Thymoglobulin will be given intravenously over a minimum of 6 hours for the first two doses and 4 hours for the subsequent dose per institutional standard practice. Doses should be based on actual body weight.

Anti-Human Thymocyte Globulin (ATG; Sangstat Medical Corp., Fremont, CA) is an immunosuppressant which alters the function of or eliminates T-cells and NK cells. Rabbit anti-thymocyte globulin (Thymoglobulin®) is a polyclonal immunoglobulin mixture (IgM/IgG) raised in rabbits against human T thymocytes which reduces all circulating lymphocytes or lymphocyte subsets. ATG is used in preparation for hematopoietic cell transplant (HCT), as immunosuppressive therapy in aplastic anemia or MDS, and for GVHD treatment.

Preparation

Thymoglobulin® is provided in 25mg vials by Sangstat. Thymoglobulin® vials should be reconstituted with 5ml sterile water to a concentration of 5mg/ml. It can then be further diluted with D5W or NS to a volume of 50ml per vial. Diluted drug should be used immediately.

Skin Test

Skin tests are not required prior to Thymoglobulin® administration.

Administration

Thymoglobulin® should be administered alone and not run piggyback with any other solution. A 0.22 micron in-line filter should be used during administration. The first and second dose of Thymoglobulin® should be infused over 6 hours, and subsequent doses should be infused over 4 hours.

Pre-Meds:

Acetaminophen, diphenhydramine, and 1 mg/kg of methylprednisolone should be given before every dose of Thymoglobulin®.

Significant Allergic Reaction Precautions

Have recommended medications for significant allergic reactions available at the bedside in case of allergic reaction:

Medication Recommendations For Significant Allergic Reactions

| | Pediatric: | Adults > 40 kg |
|--|---|---|
| Epinephrine (1:1000 dilution) [1 mg/ml] | 0.01 mg/kg IM (Every 20 minutes as needed). Maximum dose 0.3 mg | 0.3 ml SC (every 20 minutes as needed) |
| Diphenhydramine | 1 mg/kg IV (max 50 mg) | 50 mg IV |
| Hydrocortisone | 2 mg/kg IV (max 250 mg) | 250 mg IV |

4. Total Body Irradiation (TBI)

A.Cord Blood Recipients Only:

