| A: _____ | A: _____ | C: _____ | C: _____ | B: _____ | B: _____ |
| DRB1: _____ | DRB1: _____ | | | | |
| Unit #2 N/A  | | | | | |
| A: _____ | A: _____ | C: _____ | C: _____ | B: _____ | B: _____ |
| DRB1: _____ | DRB1: _____ | | | | |

Exclusion criteria:

Each of the following questions must be marked "No" Or "N/A" for the patient to enroll on 2256.

6) Yes No

Patients with Idiopathic Aplastic Anemia and Fanconi Anemia. (Patients with Aplastic Anemia associated with PNH or inherited marrow failure syndromes, except Fanconi Anemia, will be allowed).

7) Organ dysfunction. Please check yes if patient meets any of the following:

a. Yes No

Impaired cardiac function as evidenced by ejection fraction < 35% (or, if unable to obtain ejection fraction, shortening fraction <26%) or cardiac insufficiency requiring treatment or symptomatic coronary artery disease. Patients with a shortening fraction < 26% must be seen by cardiology for approval.

Date: ____ / ____ / ____

Ejection Fraction Value: ____ % Shortening Fraction Value: ____ %

b. Yes No

Impaired pulmonary function as evidenced by DLCO < 50% of predicted (or, if unable to perform pulmonary function tests, then O₂ saturation < 92% on room air).

Date: ____ / ____ / ____ DLCO Value: ____ % O₂ Saturation Value: ____ %

Protocol 2256 Eligibility (continued)

c. Yes No Impaired renal function as evidenced by creatinine-clearance < 50% for age, weight, height or serum creatinine > 2X upper normal limit or dialysis-dependent.
 Date: ____ / ____ / ____ Value: _____ mg/dL or CrCl: _____ ml/min

d. Yes No Evidence of synthetic dysfunction or severe cirrhosis requiring deferral of conditioning as recommended by a gastroenterology specialist.
 Date: ____ / ____ / ____
 ALT: _____ U/L AST: _____ U/L
 Total Bilirubin: _____ mg/dL Alk.phos: _____ U/L

8) Yes No Patients with an active infectious disease requiring deferral of conditioning; as recommended by an Infectious Disease specialist.

9) Yes No Patients who are positive for human immunodeficiency virus (HIV).

10) Yes No Females who are pregnant or breast-feeding.

11) Yes No Patients with a known hypersensitivity to treosulfan and/or fludarabine.

12) Yes No Receiving another experimental drug within 4 weeks of initiation of conditioning (day -6) unless approved by the PI..

TBI Dose Assignment

For Regimen B patients only, one of the following must be designated.

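### The hypersensitivity exclusion names treosulfan and fludarabine but omits rabbit ATG, the third conditioning drug, which every recipient is scheduled to receive

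*Combined protocol and SAP*

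**What the plan says.** Section 5B, exclusion 6, reads "Patients with a known hypersensitivity to treosulfan and/or fludarabine". Item 11 of the eligibility form in Appendix F carries the same wording. The exclusion part of that form opens with "Each of the following questions must be marked" and requires No or N/A for entry. No other inclusion or exclusion criterion mentions ATG or rabbit protein.

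Section 9 describes three conditioning drugs: treosulfan, fludarabine and rabbit ATG. On the third it says "Thymoglobulin will be administered intravenously over three consecutive days (days -4, -3, -2". The Regimen A and Regimen B tables both list it on those days with no condition on donor type or disease. It is described as a "polyclonal immunoglobulin mixture (IgM/IgG) raised in rabbits against human T thymocytes".

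On allergy to ATG, section 9 states "Skin tests are not required prior to Thymoglobulin" and instructs staff: "Have recommended medications for significant allergic reactions available at the bedside in case of allergic reaction". It also requires premedication before each dose. Section 15C describes respiratory distress, hypotension, and chest, flank or back pain as possible signs of significant allergic reaction or anaphylaxis, and says to stop the infusion.

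**The concern.** The protocol screens for hypersensitivity to its conditioning drugs, but the screen is incomplete. The omitted drug is a foreign-species protein that all patients are due to receive, and the protocol itself links it to anaphylaxis. A site that follows the form exactly would enrol a patient with a documented ATG allergy. The protocol then schedules the drug and gives no instruction for that situation.

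Patient safety is at stake, not the trial's operating characteristics. Timing adds to it. The ATG-specific precautions take effect only when the infusion is due, and by then the patient has already received myelosuppressive treosulfan. A known allergy needs to be settled before day -6.

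**Working it through.** The plan gives no figure to reproduce on this point. The check is a comparison of the eligibility text with the treatment and toxicity text.

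**Coverage of the criterion**

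| Conditioning drug | Scheduled in both regimens (section 9) | Allergy risk listed (section 15) | Bedside rescue drugs for allergic reactions ordered (section 9) | Named in exclusion 6 and item 11 |
|---|---|---|---|---|
| Treosulfan | Days -6 to -4 | Yes (15A, adult table) | No | Yes |
| Fludarabine | Days -6 to -2 | Yes (15B, rare) | No | Yes |
| Rabbit ATG | Days -4 to -2 | Yes (15C, including anaphylaxis) | Yes | **No** |

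Three of three drugs carry a listed allergy risk, and two of three are named. Total body irradiation is a fourth component, for Regimen B only, and is not a drug. The four GVHD-prophylaxis drugs (tacrolimus, methotrexate, cyclosporine, mycophenolate) have no allergy entry in section 15G. Itching and rash under tacrolimus were not counted as allergy. The same reasoning therefore does not call for adding them.

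**Is ATG really given to everyone?** Section 19 records that ATG was added to both arms, for unrelated recipients in January 2011 and for related recipients in September 2011. The adenovirus and EBV surveillance tables in section 14B treat exposure as universal. The only provision for not continuing ATG is in section 15C, and it applies once a reaction has begun.

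**Timing.** Conditioning starts on day -6 and the first ATG dose is on day -4, so the gap is 2 days. Treosulfan given by the end of day -5 is 2 × 14 g/m² = 28 g/m². Section 3C puts the marrow-suppression limit for conventional treosulfan chemotherapy at doses over 10 g/m².

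**Could an eligible patient have met ATG before?** Section 9 says ATG is used in transplant preparation, "as immunosuppressive therapy in aplastic anemia or MDS, and for GVHD treatment". Exclusion 1 states that "Patients with Aplastic Anemia associated with PNH or inherited marrow failure syndromes, except Fanconi Anemia, will be allowed", and section 5B does not exclude a previous transplant. Earlier exposure is possible. The documents do not say how often it occurs.

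**Would another step catch it?** The recommended patient history in section 14B covers prior treatment and response. Its itemised list does not include allergies, although the donor history in section 14A does. Even if the history revealed an ATG allergy, no criterion would make the patient ineligible.

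**The case against.** The strongest reply is that the protocol manages ATG allergy in more detail than that of either other drug: three-drug premedication before each dose, rescue drugs with doses, and instructions to stop the infusion. A full treatment history about a month before conditioning and the investigators' signatures on the form add a chance to catch the problem earlier. The objectives still describe a treosulfan and fludarabine regimen, which would explain the wording of exclusion 6. These points make harm less likely. They do not close the gap, because the bedside measures act from day -4 and the history and signatures have no ATG criterion to apply.

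The prior-exposure argument is also modest. The statement on ATG use is general, and idiopathic aplastic anemia is excluded. The protocol's accounts of earlier therapy in dyskeratosis congenita and Shwachman-Diamond syndrome do not list ATG. No case of known ATG allergy is reported. This stands as a reason to call the point minor.

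It can be said, too, that section 15F lists allergic reaction for cord blood infusion, so the same logic would add DMSO. That is a fair observation about a graft component, but the point here is limited to the conditioning drugs that the exclusion sets out to cover.

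Finally, an ungraded criterion might bar a patient for an earlier mild infusion reaction. Section 15C treats chills and fever separately from allergic reaction, so wording parallel to the existing criterion should not be read that way.

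**Conclusion.** The point holds as a minor patient-safety correction. The exclusion covers two of the three conditioning drugs in both places where it appears, and a patient with known ATG or rabbit-protein hypersensitivity is eligible under the rule as written. The comparison of texts is direct and needs no outside assumption. That few patients are affected is an expectation, since the documents give no count. The criterion may simply not have been updated when ATG was added in 2011. That is an inference, as no section explains the omission. Sample size, endpoints and stopping boundaries are unaffected.

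**What to change.** Add rabbit ATG (rabbit proteins) to the agents named in section 5B, exclusion 6, and make the identical change to item 11 of Appendix F. The cost is one line in each place and, rarely, a patient who becomes ineligible.

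If the sponsor would rather keep such patients and omit ATG, it needs a written rule with two parts. The first is how the patient is conditioned: without ATG the patient returns to the regimen that was amended after 5 of 13 patients (38%) had grade III-IV acute GVHD. The second is how the patient is counted: under the 2015 modification in section 19, the Regimen A subgroup accrual targets and stopping rules refer to patients who receive all three drugs. Extending the exclusion is simpler.

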6. DONOR SELECTION

Regimen A: Bone marrow or Peripheral Blood or HLA-matched sibling bone marrow combined with HLA-matched sibling cord blood

A. Inclusions: Donors must be:

1. HLA-identical related donors or
2. Unrelated donors matched for HLA-A, B, C, DRB1, and DQB1 or mismatched for a single allele at HLA-A, B, C, DRB1 or a single DQB1 antigen or allele mismatch by high resolution DNA typing.
3. PBSC is the preferred cell source (when feasible) for fully matched donors. PBSC may also be used for a mismatched donor following discussion with the PI. Bone marrow is allowed when PBSC is not feasible or as determined by the PI.
4. HLA-matched sibling bone marrow in combination with HLA-matched sibling umbilical cord blood if the HLA-matched sibling umbilical cord blood was collected and stored. The HLA-matched sibling bone marrow and cord blood would be matched for HLA-A, B, C, DRB1, and DQB1.

B. Exclusions: Ineligible donors will be those:

1. Deemed unable to undergo marrow harvesting or PBSC mobilization and leukapheresis.
2. HIV-positive.
3. With active infectious hepatitis.
4. Females with a positive pregnancy test.
5. HLA-matched sibling cord blood exclusions:
 - a. Any cord blood units that have not passed donor screening for infectious disease markers as recommended by the National Marrow Donor Project (NMDP) will not be used unless a waiver is signed by the clinical attending allowing use of cord blood unit. Cord blood units are presumed to be CMV negative regardless of serologic testing due to passive transmission of maternal CMV antibodies.

Regimen B: Unrelated Umbilical Cord Blood will be allowed if an HLA-matched related or unrelated donor is not identified or available

A. Unrelated Umbilical Cord Blood Inclusions:

1. Unit selection is based on the cryopreserved total nucleated cell (TNC) dose and matching at HLA-A, B antigen level and DRB1 allele level typing. While HLA-C antigen/allele level typing is not considered in the matching criteria, if available, may be used to optimize unit selection.
2. The patient and the cord blood unit(s) must be matched for at least 4 of 6 loci as defined above.
3. Selection of two UCB units is allowed to provide sufficient cell dose (see 3d below for algorithm to determine single versus double unit transplant). When multiple units are selected, the following rules apply:

- a. The UCB unit with the least HLA disparity (with the patient) will be selected first (i.e., selection priority is 6/6 match >5/6 match>4/6 match). Additional UCB units then may be selected to achieve the required cell dose, as outlined below (3e). If a second unit is required, this unit will be the unit that most closely HLA matches the patient and meets minimum size criteria outlined below of at least 1.5×10^7 TNC/kg (i.e. a smaller more closely matched unit will be selected over a larger less well matched unit as long as minimum criteria are met).
- b. Each UCB unit MUST contain at least 1.5×10^7 TNC per kilogram recipient weight.
- c. The total cell dose of the combined units must be at least 3.0×10^7 TNC per kilogram recipient weight.
- d. Algorithm for determining single versus double cord blood transplant: The donor selection algorithm has been designed to favor single cord HCT to decrease the risk of GVHD in the nonmalignant setting while attempting to not compromise engraftment.

| | Single Unit Allowed for: | Multiple Units Required for: |
|--------------------|-------------------------------------|---|
| Match Grade | TNC Dose | TNC Dose |
| 6/6 | $\geq 3.0 \times 10^7$ /kg | $< 3.0 \times 10^7$ /kg |
| 5/6 | $\geq 4.0 \times 10^7$ /kg | $< 4.0 \times 10^7$ /kg |
| 4/6 | $\geq 6.0 \times 10^7$ /kg | $< 6.0 \times 10^7$ /kg |

4. General Comments:

- a. Units will be selected first based on the TNC dose and HLA matching.
- b. CD34+ cell dose will not be used for unit selection unless 2 units of equal HLA- match grade and similar TNC dose ($\pm 0.5 \times 10^7$ TNC/kg) are available. In this case, the unit with the larger CD34⁺ cell dose (if data available) should be selected.
- c. A UCB unit that is 5/6 mismatched but homozygous at the locus of mismatch should be chosen over a 5/6 unit with bidirectional mismatch even if the latter unit is larger (has more cells). This also applies to 4/6 units. This is only applicable to choosing units within a given match grade.
- d. Within an HLA match grade, the unit containing the greatest number of cells will be chosen. If there are two units of equivalent cell dose ($\pm 0.5 \times 10^7$ TNC/kg) within a match level, choose the unit with match by higher resolution molecular typing, if known.
- e. Other factors to be considered:
 1. Within the same HLA match grade, matching at DR takes preference.
 2. Cord blood banks located in the United States are preferred.
 3. The youngest unit would be preferred.

B. Unrelated UCB Unit Exclusions:

1. Any cord blood units with $<1.5 \times 10^7$ total nucleated cells per kilogram recipient weight.
2. Any cord blood units that have not passed donor screening for infectious disease markers as recommended by NMDP will not be used unless a waiver is signed by the clinical attending allowing use of cord blood unit. Cord blood units are presumed to be CMV negative regardless of serologic testing due to passive transmission of maternal CMV antibodies.

7. INFORMED CONSENT

The attending physician will conduct a conference with the patient and family to discuss this study and alternative treatments available. In a separate conference, the risks of the donation procedure will be outlined to the donor and/or his parent/guardian(s), including the risks of anesthesia, bleeding, and infection. The goals of the study, requirement for data collection, and requirement for release of medical records will be discussed with the patient and/or his/her parent/guardian. All potential risks associated with the use of treosulfan, fludarabine, low dose TBI (cord only), immunosuppressive drugs and allogeneic HCT will be discussed as objectively as possible. Discussion of potential complications should include graft rejection, GVHD, infections, and death.

Informed consent from the patient and donor will be obtained using forms approved by the Institutional Review Board of the Fred Hutchinson Cancer Research Center. Informed consent will be obtained by the Principal Investigator, Co-Investigator, or Attending Physician who is familiar with the study but not necessarily an investigator. When patients are less than 18 years of age, consent will be obtained from parents or legal guardian(s). All patients enrolled at collaborating centers will engage in institution-specific informed consent conferences after completion of the pre-transplant evaluation. Informed consent from the donor and patient will be obtained using a form approved by the Institutional Review Board for each treatment center.

8. PROTOCOL REGISTRATION

8A. FHCRC Patients: Eligible patients will be identified by the Clinical Coordinator's Office who will register patients with the Registration office [contact]) between 8:30 am and 4:00 PM, Monday through Friday. After hours, the Registration Office can be reached by paging [contact]

8B. Collaborating Institutions: Eligible patients will be identified by the principal investigator of the collaborating institution who will register the patient with the FHCRC Registration Office. Registration will include completion of the eligibility checklist and demographic form (**Appendix F of protocol**). This form and a copy of the signed informed consent will be faxed to the Trial Coordinator [contact]). Questions regarding eligibility or protocol information should be directed to the Principal Investigator, [name] [contact].

9. PLAN OF TREATMENT/CONDITIONING REGIMEN:

| Regimen A: For patients receiving marrow, PBSC or HLA-matched sibling bone marrow combined with HLA-matched sibling cord blood | | |
|---|---|--|
| Day | Treatment | Dose |
| -6 | Treosulfan | 14 grams/m ² /day IV ^a |
| | Treosulfan PK sampling ^b | |
| | Fludarabine | 30 mg/m ² /day IV ^a |
| -5 | Treosulfan | 14 grams/m ² /day IV ^a |
| | Treosulfan PK sampling ^c | |
| | Fludarabine | 30 mg/m ² /day IV ^a |
| -4 | Treosulfan | 14 grams/m ² /day IV ^a |
| | Fludarabine | 30 mg/m ² /day IV ^a |
| | Rabbit Antithymocyte globulin (ATG; Thymoglobulin®) | 1.0 mg/kg/day IV ^d |
| -3 | Fludarabine | 30 mg/m ² /day IV ^a |
| | Rabbit Antithymocyte globulin (ATG; Thymoglobulin®) | 2.5 mg/kg/day IV ^d |
| -2 | Fludarabine | 30 mg/m ² /day IV ^a |
| | Rabbit Antithymocyte globulin (ATG; Thymoglobulin®) | 2.5 mg/kg/day IV ^d |
| -1 | Rest ^e | |
| 0 | Marrow or PBSC infusion or HLA-matched sibling bone marrow combined with HLA-matched sibling cord blood | |

^a For patients >120% ideal body weight (IBW) BSA will be calculated using adjusted weight

^b Research Treosulfan PK sampling (7 timepoints): All patients, see **section 14B.7** for details

^c Research Treosulfan PK sampling (7 timepoints): Only in patients who are < 4 years of age at time of start of conditioning, see **section 14B.7** for details.

^d Actual body weight

^e Additional rest days may be added given delays that may occur with stem cell collection, transportation or processing. The actual day of stem cell infusion will remain “Day 0” even if 1-2 days later than originally scheduled

| Regimen B: For patients receiving unrelated umbilical cord blood | | |
|---|---|--|
| Day | Treatment | Dose |
| -6 | Treosulfan | 14 grams/m ² /day IV ^a |
| | Treosulfan PK sampling ^b | |
| | Fludarabine | 30 mg/m ² /day IV ^a |
| -5 | Treosulfan | 14 grams/m ² /day IV ^a |
| | Treosulfan PK sampling ^c | |
| | Fludarabine | 30 mg/m ² /day IV ^a |
| -4 | Treosulfan | 14 grams/m ² /day IV ^a |
| | Fludarabine | 30 mg/m ² /day IV ^a |
| | Rabbit Antithymocyte globulin (ATG; Thymoglobulin®) | 1.0 mg/kg/day IV ^d |
| -3 | Fludarabine | 30 mg/m ² /day IV ^a |
| | Rabbit Antithymocyte globulin (ATG; Thymoglobulin®) | 2.5 mg/kg/day IV ^d |
| -2 | Fludarabine | 30 mg/m ² /day IV ^a |
| | Rabbit Antithymocyte globulin (ATG; Thymoglobulin®) | 2.5 mg/kg/day IV ^d |
| -1 | Recipients with underlying T-cell primary | TBI 200 cGy |
| | Immunodeficiency or | |
| | All other recipients | TBI 300 cGy |
| 0 | Unrelated umbilical cord blood infusion | |

^a For patients >120% ideal body weight (IBW) BSA will be calculated using adjusted weight

^b Research Treosulfan PK sampling (7 timepoints): All patients, see **section 14B.7** for details

^c Research Treosulfan PK sampling (7 timepoints): Only in patients who are < 4 years of age at time of start of conditioning, see **section 14B.7** for details.

^d Actual body weight

Conditioning regimen.**The regimen will consist of:****1. Treosulfan.**

Treosulfan will be administered intravenously over 120 minutes for three consecutive days (day -6 to -4). Use actual weight to calculate BSA. For patients >120% of ideal weight, use adjusted weight to calculate BSA. Optional pharmacokinetic evaluation will be performed on days -6 (all patients) and -5 (only in patients who are < 4 years of age at time of start of conditioning; see Section 14B.7).

Treosulfan will be supplied to investigators by Medac GmbH, Hamburg Germany under an IND held by Fred Hutchinson Cancer Research Center (IND 72,479). The drug will be delivered by courier to each participating centers' pharmacy as a clinical investigational product with a study-specific label on the glass vial, as approved by the FDA. Treosulfan is available as a white crystalline powder in vials of 1000 mg and 5000 mg. The dry product must be stored at room temperature and has a shelf life of 5 years. TREO must be dissolved in 20 ml (1 g vial) or 100 ml (5g vial) of 0.45% sodium chloride solution, for injection for a final concentration of 50 mg/ml. The 0.45% sodium chloride must be warmed to 25-30°C (not higher) using a warmer or water bath. The reconstituted solution should remain at room temperature and be used the day of preparation. The reconstituted solution should not be stored in a refrigerator because crystallization may occur at low temperatures. Acidic media do not influence the stability of treosulfan. In alkaline and neutral solutions treosulfan decomposes to methanesulfonic acid and threitol. The reconstituted solution has a physicochemical stability of at least 1 day when stored at room temperature in the original glass bottle.

There have been isolated reports of seizure in infants after combined administration of Treosulfan with Fludarabine or cyclophosphamide. Therefore, seizure prophylaxis during Treosulfan administration should be considered for patients ≤ 1 year of age. We recommend the following: for patients ≤ 1 year begin levetiracetam (Keppra) at 10 mg/kg every 12 hours to start the evening prior to Treosulfan administration and continue until 24 hours after the infusion.

2. Fludarabine.

Fludarabine will be administered intravenously at a dose of 30 mg/m²/day over 60 minutes for five consecutive days (day -6 to -2). On days -6 to -4, fludarabine will be given after the treosulfan dose is given. For patients > 120% of ideal weight, BSA will be calculated using adjusted weight. Fludarabine (Fludara®, Berlex Laboratories, Inc., Richmond, CA) is commercially available in the U.S. Details of the product's description, preparation; storage and stability are found in the drug's package insert.

3. Rabbit Anti-thymocyte globulin (ATG; Thymoglobulin®)

Thymoglobulin will be administered intravenously over three consecutive days (days -4, -3, -2) at a dose of 1.0 mg/kg on day -4, and then 2.5 mg/kg on days -3 and -2 for a total dose of 6.0 mg/kg. Thymoglobulin will be given intravenously over a minimum of 6 hours for the first two doses and 4 hours for the subsequent dose per institutional standard practice. Doses should be based on actual body weight.

Anti-Human Thymocyte Globulin (ATG; Sangstat Medical Corp., Fremont, CA) is an immunosuppressant which alters the function of or eliminates T-cells and NK cells. Rabbit anti-thymocyte globulin (Thymoglobulin®) is a polyclonal immunoglobulin mixture (IgM/IgG) raised in rabbits against human T thymocytes which reduces all circulating lymphocytes or lymphocyte subsets. ATG is used in preparation for hematopoietic cell transplant (HCT), as immunosuppressive therapy in aplastic anemia or MDS, and for GVHD treatment.

Preparation

Thymoglobulin® is provided in 25mg vials by Sangstat. Thymoglobulin® vials should be reconstituted with 5ml sterile water to a concentration of 5mg/ml. It can then be further diluted with D5W or NS to a volume of 50ml per vial. Diluted drug should be used immediately.

Skin Test

Skin tests are not required prior to Thymoglobulin® administration.

Administration

Thymoglobulin® should be administered alone and not run piggyback with any other solution. A 0.22 micron in-line filter should be used during administration. The first and second dose of Thymoglobulin® should be infused over 6 hours, and subsequent doses should be infused over 4 hours.

Pre-Meds:

Acetaminophen, diphenhydramine, and 1 mg/kg of methylprednisolone should be given before every dose of Thymoglobulin®.

Significant Allergic Reaction Precautions

Have recommended medications for significant allergic reactions available at the bedside in case of allergic reaction:

Medication Recommendations For Significant Allergic Reactions

| | Pediatric: | Adults > 40 kg |
|--|---|---|
| Epinephrine (1:1000 dilution) [1 mg/ml] | 0.01 mg/kg IM (Every 20 minutes as needed). Maximum dose 0.3 mg | 0.3 ml SC (every 20 minutes as needed) |
| Diphenhydramine | 1 mg/kg IV (max 50 mg) | 50 mg IV |
| Hydrocortisone | 2 mg/kg IV (max 250 mg) | 250 mg IV |

4. Total Body Irradiation (TBI)

A.Cord Blood Recipients Only:

Patients with an underlying T-cell immunodeficiency will receive 200 cGy TBI on day -1. All other patients will receive 300cGY TBI on day – 1. See institutional standard practice guidelines for radiation (**Appendix B**).

